3.3.4 Replacement of Subjects

Subjects who discontinue from the study will not be replaced.

3.4 Treatments

3.4.1 Details of Study Treatments and Storage Conditions

The test product is defined as AfreZZa [insulin human] inhalation powder administered using the inhaler ([Table 1](#)).

Table 1: Test Product (Afrezza)

Test Product	
Trade Name	Afrezza®
Nonproprietary Name	Technosphere® Insulin inhalation powder and Gen2C inhalation system
Manufacturer	MannKind Corporation
Active Ingredient	Human insulin, recombinant DNA origin
Formulation	Inhalation powder Each milligram of formulation contains 3.0 units of human insulin.
Route	Oral inhalation The inhaler is breath-powered by the subject. When the subject inhales through the device, the powder is aerolized and delivered to the lung.
Dose(s)	Individualized; See Section 3.5.2.2.1.1 (Visit 2) and Section 3.5.2.2.2.1 (Visit 3) for guidelines.
Storage (Not in Use)	Refrigerated at 2°C to 8°C (36°F to 46°F) Note: The inhaler should be at room temperature for 10 minutes before use.
Storage (In Use)	
 Room temperature storage 25°C (77°F) Excursions permitted to 15 to 30°C (59°F to 86°F) Sealed (unopened) blister card: Must be used within 10 days Opened strip: Must be used within 3 days
Packaging	Blister card containing 15 cartridges. Two blister cards are overwrapped in a foil pouch.
Strength(s)	Pre-metered single-dose 4-, 8-, and 12-unit cartridges will be provided.
Lot and Batch Numbers	Will be recorded in the study master file and provided in the final clinical study report

In addition, subjects will take their personal basal insulin while enrolled in the study. The dose and type of basal insulin should not be changed between Visits 1 and 3.

Basal insulin therapy administered via either SC injection or pump will be permitted, but pumps cannot be in automated insulin delivery mode for the 3 hours before or during Visits 2 or 3.

3.4.2 Dosage Schedule

Subjects will administer Afrezza at Visits 2 and 3, at the start of a meal challenge, according to the dosing guidelines provided in Section 3.5.2.2.1.1 (Visit 2) and Section 3.5.2.2.2.1 (Visit 3).

3.4.3 Treatment Assignment

All subjects in this study will receive Afrezza at Visits 2 and 3.

Subjects in this study will be assigned a unique subject identification number. Once screening procedures are complete, eligible subjects will be enrolled.

3.4.4 Drug Packaging and Blinding

This is an open-label clinical study. Neither clinical site personnel nor subjects will be blinded to treatment.

3.4.5 Drug Inventory and Accountability

The Investigator or designee is responsible for maintaining AfreZZa and inhaler accountability records to ensure appropriate distribution throughout the clinical study. Investigators should maintain records that document adequately that the subjects were provided the doses specified by the protocol and reconcile all AfreZZa and inhalers received at the site before final disposition. At the end of the study, or as directed, all AfreZZa and inhalers, including unused, partially used, and empty containers will be discarded.

3.4.6 Treatment Compliance

It is expected that subjects will be compliant with all dosing instructions and subjects will administer both doses of AfreZZa under clinical supervision at the study site.

3.4.7 Prior and Concomitant Illnesses and Treatments

3.4.7.1 Prior and Concomitant Illnesses

Illnesses present at screening will be considered to be prior illnesses (medical history). The subject's history of diabetes should be recorded at screening on the CRF. Subjects will also be questioned about drug and environmental allergies, family pulmonary disease history, and their smoking status/exposure to pulmonary toxins. Investigators (or their designee) should document all other significant illnesses that the subject has experienced within 6 months of screening as medical history on the CRF.

After enrollment, any new or worsening illnesses should be documented as AEs in the CRF.

3.4.7.2 Concomitant Treatments

Any medication or therapy that is taken by or administered to the subject during the course of the study must be recorded in the CRF. The entry must include the dose, regimen, route, indication, and dates of use.

Concomitant treatments, defined as treatments taken after enrollment, include all nonstudy treatments that are taken by subjects at any time during the clinical study, including prescription drugs, herbal supplements, or over-the-counter medications, should be recorded as concomitant medications.

Antidiuretic drugs (e.g., beta blockers and clonidine) are prohibited during the study. Subjects should continue their prestudy antihyperglycemic medications but no changes to their medications should be made between Visits 1 and 3. The initiation of drugs or herbal

preparations known to modify glucose metabolism that may, in the opinion of the Investigator, interfere with the clinical study results should be discussed with the medical monitor.

3.5 Assessments

Unless otherwise indicated, all assessments will be performed by the Investigator or a qualified designee.

3.5.1 Schedule of Assessments

The procedures to be performed throughout the study are outlined in the Schedule of Assessments ([Table 2](#)).

Table 2: Schedule of Assessments

Clinic Visit	Screening	Treatment Period			Follow-up	Early Termination
	Visit 1 ^a	Visit 2	Visit 3	Visit 4		
Day	Up to 7 days before Visit 2	1	Day 4	Day 7		
Visit Window		NA	+/- 2 days	+/- 2 days		
Informed consent	X					
COVID-19 screening assessment ^b	X					
Demographics and medical history	X					
Eligibility criteria confirmed and subject registration	X					
Vital signs measurement	X					
Complete physical examination and record height and weight	X					
Record concomitant medications	X	X	X	X		X
Smoking status and evaluation of pulmonary toxin exposure	X					
Laboratory assessments						
HbA1c	X					
Urine pregnancy test ^c	X					
Education, treatment, and clinic assessments						
Training on the use of AfreZZa with BluHale PRO		X	X			
Dose of AfreZZa with standardized meal ^d		X	X			
SMBG measurements ^e		X	X			
CGM readings, if applicable ^f		X	X			
FEV ₁ measurement	X	X ^g	X ^g	X		X
Collect and review glucose meter data		X	X			
Record AEs	X ^h	X	X	X		X
Record any hypoglycemic episodes ⁱ		X	X			
Provide discharge instructions to the subject		X	X			

AE=adverse event, BMI=body mass index, CGM=continuous glucose monitor, COVID-19=coronavirus 2019, CRF=case report form, FEV₁=forced expiratory volume in 1 second, HbA1c=glycated hemoglobin A1c, SMBG=self-monitored blood glucose.

Note: Subjects should arrive to the clinic in a fasting state for Visits 2 and 3, with exception of treating hypoglycemia. Fasting is defined as no intake of drink or food, with exception of water, for ≥ 6 hours before the clinic visit.

- Visits 1 and 2 may be consolidated into a single clinic visit, provided the subject is in a fasting state and able to complete all assessments required for both visits.
- Subjects will be asked to provide a recent negative COVID-19 test (if available), confirm they have no symptoms of COVID-19, or provide evidence of COVID-19 vaccination.
- A negative urine pregnancy test is required for enrollment, from all female subjects of child-bearing potential. After enrollment, additional pregnancy tests may be conducted as needed at the discretion of the Investigator.

- d. The subject's SMBG value must be between 100 and 200 mg/dL without requiring a correction dose of bolus insulin in order to receive the AfreZZa dose and complete the meal challenge.
- e. Subjects should use their Sponsor-provided blood glucose meter to take SMBG values: 15 minutes before their AfreZZa dose, immediately before administering their dose of AfreZZa (t=0; baseline) and at 15, 30, 45, 60, 90 and 120 minutes after AfreZZa dosing. Additional SMBG measurements may be taken per Investigator discretion.
- f. If the subject is wearing a CGM, they will be asked to write down their CGM value every time they take an SMBG measurement in the clinic. These CGM values will be entered in the CRF completed at Visit 2 and Visit 3.
- g. At the beginning of Visits 2 and 3, before their dose of AfreZZa, subjects will have FEV₁ measurements taken in the clinic. After completion of the standardized meal challenge (120 minutes after AfreZZa dose), subjects will have another FEV₁ measurement before leaving the clinic.
- h. Any AE that occurs after the subject enrolls in the study (consent date) will be recorded.
- i. Hypoglycemic episodes will be defined as all SMBG measurements <70 mg/dL. See Section [3.5.5.6](#).

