3.5.5.6 Hypoglycemic Events

A hypoglycemic episode is defined as any event with SMBG <70 mg/dL (i.e., Level 1 hypoglycemia) or SMBG <54 mg/dL (i.e., Level 2 hypoglycemia). Severe hypoglycemic events are defined as events requiring assistance of another person to actively administer carbohydrate, glucagon, or other resuscitative actions. Severe hypoglycemic events will be documented as SAEs in the CRF. Nonsevere hypoglycemic events will not be documented as AEs but will be recorded in the hypoglycemia page of the CRF.

After the standardized meal challenges at Visit 2 and Visit 3, subjects will be monitored for signs of hypoglycemia. Subjects exhibiting signs of hypoglycemia will be treated as appropriate (e.g., provided with a snack or glucose) and the type of treatment given and time will be recorded. If a subject experiences hypoglycemia, SMBG measurements should be performed every 15 minutes until hypoglycemia is resolved.

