5.2.12 Safety Analyses

The incidence of hypoglycemia (total, nocturnal, and severe) and number of hypoglycemic episodes will be summarized. Summary tables providing frequency counts and the percentage of subjects within each category will be provided for Level 1 hypoglycemia (SMBG <70 mg/dL)

and Level 2 hypoglycemia (SMBG <54 mg/dL). Exposure-adjusted incidence rates and exposure-adjusted event rates will be calculated and summarized.

The number and percentage of subjects with TEAEs will be tabulated by system organ class and preferred term by relationship to treatment and by severity.

A summary table by study visit with descriptive statistics for FEV₁ at all time points will be provided. The FEV₁ data will also be presented graphically.

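### Table 2 footnote i counts every SMBG reading below 70 mg/dL as a hypoglycemic episode and no rule merges consecutive low readings, so event counts and rates depend on duration and testing frequency

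*Combined protocol and SAP*

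**What the plan says.** Two places in the protocol define a hypoglycemic episode.

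- Table 2, footnote i (Section 3.5.1), attached to the row for recording hypoglycemic episodes: "Hypoglycemic episodes will be defined as all SMBG measurements <70 mg/dL". The footnote then refers the reader to Section 3.5.5.6.
- Section 3.5.5.6: "A hypoglycemic episode is defined as any event with SMBG <70 mg/dL (i.e., Level 1 hypoglycemia) or SMBG <54 mg/dL (i.e., Level 2 hypoglycemia". Level 1 has no lower bound, so a value below 54 mg/dL meets both levels.

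Two provisions govern how many readings are taken. Section 3.5.5.6 requires that, once a subject is low, "SMBG measurements should be performed every 15 minutes until hypoglycemia is resolved". Footnote e to Table 2 sets post-dose readings "at 15, 30, 45, 60, 90 and 120 minutes after AfreZZa dosing" and adds: "Additional SMBG measurements may be taken per Investigator discretion".

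Section 2.2 makes both event rates and incidence of Level 1 and Level 2 hypoglycemia, within 120 minutes of dosing, measures of the secondary safety objective. Section 5.2.12 says that the "number of hypoglycemic episodes will be summarized" and that exposure-adjusted event rates will be calculated. No section says when an episode starts or ends, how consecutive low readings are combined, or what unit of exposure is used.

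**The concern.** The unit in footnote i is the measurement. A low triggers further measurements under the retesting rule, and each one still below 70 mg/dL meets the footnote again. The count then reflects three things at once: how many lows occurred, how long each lasted, and how often staff tested.

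The study sets the labeled dose against a higher one in the same subjects, with 20 planned completers, open label. Readers will put the Visit 2 and Visit 3 rates side by side. With so few subjects, one or two long lows could dominate a reading-based count, and discretionary testing could differ between visits because staff know the dose. A difference in such rates could not be read as a difference in the number of episodes.

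The wording also leaves room for two analysts, or two sites completing the hypoglycemia page of the CRF, to produce different counts from identical readings.

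**Working it through.** The plan states no expected event count or rate, so there is no figure to reproduce. The check is a direct count.

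**Inputs from the protocol.** Scheduled post-dose readings at 15, 30, 45, 60, 90 and 120 minutes (Table 2, footnote e); retesting every 15 minutes during a low (Section 3.5.5.6); 2 hours of supervised observation per dose (Sections 3.5.2.2.1.1 and 3.5.2.2.2.1); 20 completers (Section 5.2.3).

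**Assumed for illustration.** The number and length of lows, and 2 hours of exposure per subject per visit.

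**Step 1: readings per continuous low.** Take a low first detected at 60 minutes. Retesting adds readings at 75 and 105 minutes while the low persists.

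| Last low reading (min) | Low readings, scheduled times only | Low readings with retesting | Episodes if merged |
|---|---|---|---|
| 60 | 1 | 1 | 1 |
| 75 | 1 | 2 | 1 |
| 90 | 2 | 3 | 1 |
| 105 | 2 | 4 | 1 |
| 120 | 3 | 5 | 1 |

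The extreme case, low from 15 to 120 minutes, gives 8 low readings, 6 of them scheduled, for one episode. Discretionary readings would add to these counts.

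**Step 2: effect on a rate.** Exposure per visit = 20 × 2 h = 40 person-hours. With 4 episodes (assumed), the episode rate is 4/40 = 0.10 per hour, however long the lows last. The reading-based rate is 4 × m/40, where m is the number of low readings per episode:

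- m = 1: 0.10
- m = 2: 0.20
- m = 3: 0.30
- m = 5: 0.50
- m = 8: 0.80

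If the 4 episodes occur in 4 subjects, incidence is 4/20 = 20% in every case.

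**Step 3: effect on the comparison of visits.** With equal numbers of episodes at both visits, the apparent ratio of Visit 3 to Visit 2 is m at Visit 3 divided by m at Visit 2. The true episode ratio is 1.0 throughout.

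- 2 readings at each visit: 8/8 = 1.0, no distortion
- 2 at Visit 2 and 3 at Visit 3 (4 episodes each): 12/8 = 1.5
- 1 at Visit 2 and 3 at Visit 3 (3 episodes each): 9/3 = 3.0
- 3 at Visit 2 and 2 at Visit 3 (4 episodes each): 8/12 = 0.67

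Distortion needs a difference in m between visits, and it can go in either direction.

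**Step 4: the two levels.** A low reading 68, 52, 60 and then 75 mg/dL gives three Level 1 counts and one Level 2 count by readings. Merged, it is one episode in a cumulative below-70 row and one in the below-54 row.

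**The case against.** The strongest reply is that footnote i is not the counting rule. It annotates a row about recording, so it can be read as the threshold for making an entry. It sends the reader to Section 3.5.5.6, and Section 3.5.2 says that assessments are described in detail in Sections 3.5.4 and 3.5.5. Section 3.5.5.6 uses event language and describes a hypoglycemia that runs over several readings until it resolves. Nonsevere events, not readings, go on the CRF page, and Section 5.2.12 summarizes episodes. Lows are also treated, which may keep runs of low readings short.

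This shows that the authors may well have had episodes in mind. It does not supply a merging rule, and the only explicit statement of what counts as an episode remains the reading-based one in footnote i. The two wordings still have to be reconciled.

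A reader might infer more than the text supports on three points:

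- **That the plan's rate ratio between doses is wrong.** Section 5.2.12 plans descriptive summaries only. It specifies no ratio, test or model.
- **That the inflation will be larger at the higher dose.** Longer lows or more testing at Visit 3 are plausible, but the documents give no evidence on either.
- **That an event below 54 mg/dL is improperly double-counted.** The thresholds of 70 and 54 are used consistently as cumulative cut-offs, and no section adds the two rows together.

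**Conclusion.** The point holds for the number of episodes and for the exposure-adjusted event rates. Footnote i, applied as written together with the retesting rule, turns one continuous low into up to five counts if it is first detected at 60 minutes, and up to eight if it is present from 15 minutes, before any discretionary tests. The descriptive comparison of the two doses can therefore be distorted.

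The apparent ratios of 1.5 and 3.0 rest on assumed episode numbers and assumed readings per episode. The actual size cannot be estimated from the documents, and it would be nil if readings per episode were the same at both visits. It is also not established that the sponsor will count readings: Section 5.2.12 does not say so, and that result follows from a literal reading of the footnote.

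Subject incidence is not inflated by repeat readings. Severe hypoglycemia is defined by the need for assistance, so it is not affected either. The nested Level 1 and Level 2 thresholds are acceptable if the tables label them as cumulative. The correction should be made before database lock.

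**What to change.** Replace footnote i and align Section 3.5.5.6 with a single definition, for analysis only:

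- Consecutive SMBG readings below 70 mg/dL form one episode. It runs from the first reading below 70 to the first later reading of 70 or above or, if the subject is still low, to the end of the 120-minute window.
- Each episode is counted once in the Level 1 (below 70 mg/dL) row, labeled cumulative. It is also counted once in the Level 2 row if its lowest value is below 54 mg/dL. The two rows are not added.
- Section 5.2.12 states that the number of episodes and the event rates use this definition.

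This keeps the protocol's Level 1 and Level 2 thresholds and leaves retesting, treatment of lows and visit procedures untouched.

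The cost is a short text change and a small derivation from readings already collected. One limitation remains: a brief rebound across 70 mg/dL, such as 68, 71, 69, would still split into two episodes, so some dependence on testing frequency persists and should be acknowledged when the rates are reported.

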3.5.2 Study Procedures

Subject consent will be obtained at screening before any clinical study procedures are performed.

Procedures will be performed at the visits indicated in the Schedule of Assessments ([Table 2](#)). A detailed description of each assessment can be found in Sections [3.5.4](#) (efficacy) and [3.5.5](#) (safety).

3.5.2.1 Screening (Visit 1)

Subject consent will be obtained upon screening before any study procedures are performed.

The following will be performed at Visit 1:

- Record demographics and medical history (see Section [3.5.5.1](#))
- Record vital signs (see Section [3.5.5.4](#))
- Perform complete physical examination (see Section [3.5.5.2](#))
- Record height and weight (see Section [3.5.5.3](#))
- Record concomitant medications (see Section [3.4.7.2](#))
- Record smoking status and pulmonary toxin exposure
- Measure and record FEV₁
- Collect blood and urine for laboratory tests (see Section [3.5.5.7](#))
- Perform COVID-19 screening assessment
- Enrollment (if eligibility criteria are met)

Visits 1 and 2 may be consolidated into a single clinic visit, provided the subject is in a fasting state and able to complete all assessments required for both visits.

3.5.2.2 Treatment Period

Subjects will come into the clinic in a fasting state for Visits 2 and 3, with exception of treating hypoglycemia. Fasting will be defined as no intake of drink or food, with exception of water, for ≥ 6 hours before the clinic visit.

Subjects must have an SMBG value between 100 and 200 mg/dL without requiring a correction dose of bolus insulin in order to receive each AfreZZa dose and complete the meal challenges.

Subjects using an insulin pump will be instructed to make sure their insulin pump is not in the automated insulin delivery mode for the 3 hours before and during treatment visits. Subjects will also be instructed not to inject correction doses of bolus insulin during the 6 hours immediately preceding each AfreZZa dose. If the subject requires a bolus insulin injection to correct hyperglycemia within the 6 hours prior to the scheduled visit, the meal challenge will need to be rescheduled. An SMBG measurement will be taken 15 minutes before the expected dose of AfreZZa so the Investigator can assess if the subject is within the required SMBG range (100 to 200 mg/dL). If the subject's SMBG value is <100 mg/dL, the Investigator can provide 15 g of fast-acting carbohydrates and remeasure SMBG after 30 minutes to determine if the subject should proceed to the meal challenge. The SMBG value obtained immediately before each dose of AfreZZa (t=0) will be used to determine if the subject can proceed to the meal challenge and will serve as the baseline value for that visit.

Each meal challenge will consist of 1 to 2 bottles of nutritional shake to be fully consumed within 15 minutes. The nutritional shake will contain approximately 240 calories, 41 g carbohydrate, 10 g protein, and 4 g fat per bottle. Each AfreZZa dose will be administered at the start of the meal challenge.

3.5.2.2.1 Visit 2

The following procedures will be performed at Visit 2:

- Record concomitant medications (see Section 3.4.7.2)
- Complete training on the AfreZZa inhaler using BluHale® PRO
- Measure and record FEV₁ before AfreZZa dose
- Take first dose of AfreZZa with standardized meal challenge according to Section 3.5.2.2.1.1
- Measure and record FEV₁ after completion of the meal challenge
- Record AEs
- Collect and review glucose meter data
- Record any hypoglycemic episodes (see Section 3.5.5.6)
- Provide discharge instructions to the subject

3.5.2.2.1.1 Standardized Meal Challenge and AfreZZa Dosing at Visit 2

The AfreZZa dose to be taken at Visit 2 will be based on the dose of RAA that the subject would normally take, converted according to the guidelines provided in the current AfreZZa PI as shown in Table 3.

For AfreZZa doses exceeding 12 units, inhalations from multiple cartridges are necessary. To achieve the required total mealtime dose, subjects should use a combination of 4-unit, 8-unit, and 12-unit cartridges.

Table 3: Dose of AfreZZa at Visit 2

RAA Dose (Units)	AfreZZa Dose (Units)
Up to 4	4
5	8
6	
7	
8	
9	12
10	
11	
12	
13	16
14	
15	
16	
17	20
18	
19	
20	
21	24
22	
23	
24	

RAA=rapid-acting insulin analog (e.g., insulin aspart or insulin lispro)

Note: There is no maximum dose of AfreZZa and the required total mealtime dose may differ from the examples provided in this table.

The dose of AfreZZa will be administered at the start of the meal challenge. The subject must consume 1 to 2 bottles of nutritional shake within 15 minutes for the meal challenge and take SMBG measurements 15 minutes before their AfreZZa dose, immediately before administering the AfreZZa dose ($t=0$; baseline) and at 15, 30, 45, 60, 90, and 120 minutes after AfreZZa dosing. The subject will remain under clinical supervision for the 2 hours after their dose of AfreZZa.

If the subject is wearing a continuous glucose monitor (CGM), they will be asked to write down their CGM value every time they take an SMBG measurement in the clinic. These CGM values will be entered in the CRF completed at Visit 2.

After completing the standardized meal challenge, the Investigator will decide, based on the subject's glucose excursion at Visit 2 if the subject should proceed to Visit 3 where a titrated dose of AfreZZa will be administered according to [Table 4](#).

3.5.2.2.2 Visit 3

The following procedures will be performed at Visit 3:

- Record concomitant medications (see Section [3.4.7.2](#))
- Complete refresher training on the Afrezza inhaler using BluHale PRO
- Measure and record FEV₁ before Afrezza dose
- Take the dose of Afrezza with standardized meal challenge according to Section [3.5.2.2.1.1](#)
- Measure and record FEV₁ after completion of the meal challenge
- Record AEs
- Collect and review glucose meter data
- Record any hypoglycemic episodes (see Section [3.5.5.6](#))
- Provide discharge instructions to the subject

3.5.2.2.2.1 Standardized Meal Challenge and Afrezza Dosing at Visit 3

The Afrezza dose to be taken at Visit 3 will be based on the dose of RAA that the subject would normally take, converted by multiplying their RAA dose by 2 and rounding down to the nearest Afrezza cartridge size as shown in [Table 4](#). If the subject's normal RAA dose is <4 units, the subject will be asked to consume enough nutritional shake, per their normal insulin:carbohydrate ratio, to cover an RAA dose of ≥ 4 units such that their Afrezza dose at Visit 3 is higher than the dose taken at Visit 2.

For Afrezza doses exceeding 12 units, inhalations from multiple cartridges are necessary. To achieve the required total mealtime dose, subjects should use a combination of 4-unit, 8-unit, and 12-unit cartridges.

Table 4: Dose of AfreZZa at Visit 3

RAA Dose (Units)	AfreZZa Dose (Units)
<4	4
4	8
5	
6	12
7	
8	16
9	
10	20
11	
12	24
13	
14	28
15	
16	32
17	
18	36
19	
20	40
21	
22	44
23	
24	48

RAA=rapid-acting insulin analog (e.g., insulin aspart or insulin lispro)

Note: There is no maximum dose of AfreZZa and the required total mealtime dose may differ from the examples provided in this table.

The dose of AfreZZa will be administered at the start of the meal challenge. The subject must consume 1 to 2 bottles of nutritional shake within 15 minutes for the meal challenge and take SMBG measurements 15 minutes before their AfreZZa dose, immediately before administering the AfreZZa dose (t=0; baseline) and at 15, 30, 45, 60, 90, and 120 minutes after AfreZZa dosing. The subject will remain under clinical supervision for the 2 hours after their dose of AfreZZa.

If the subject is wearing a CGM, they will be asked to write down their CGM value every time they take an SMBG measurement in the clinic. These CGM values will be entered in the CRF completed at Visit 3.

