1.2 Study Rationale

The current study aims to evaluate 2 different doses of Afrezza in adults ≥ 18 years of age. Subjects will administer an Afrezza dose based on the current prescribing information (PI) with a meal challenge, and then proceed to a second meal challenge where a second Afrezza dose will be administered based on the subject's RAA dose multiplied by 2 and rounded down to the nearest Afrezza cartridge size, subject to Investigator discretion.

Pooled Afrezza trial data suggests that subjects achieve similar glycemic control with a dose ratio of 1.5- to 2-fold the equivalent unit value of a SC insulin analog in head-to-head comparisons (Kendall et al. 2020, Grant et al. 2019). Thus, the Sponsor has chosen to evaluate 2 different doses of Afrezza to assess whether a higher dose results in improved postprandial glucose control.

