2 STUDY OBJECTIVES

2.1 Primary Objective

The primary objective of this study is:

- To evaluate the efficacy of Afrezza administered at 2 different doses, combined with basal insulin, in adults 18 years and older with T1DM or T2DM as measured by:
 - Mean change from baseline in postprandial glucose based on self-monitored blood glucose (SMBG) from immediately before administering the dose of Afrezza (t=0; baseline) to 15, 30, 45, 60, 90 and 120 minutes after Afrezza dosing in conjunction with a standardized meal challenge

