5.2.1 General Considerations

All statistical processing will be performed using the most current version of SAS® software (SAS Institute Inc, Cary, NC) at the time of the analysis. Summary tables (descriptive statistics and/or frequency tables) will be provided for screening and/or baseline variables, efficacy variables, and safety variables. Continuous variables will be described by descriptive statistics (n, mean, median, standard deviation, minimum, and maximum). Frequency counts and percentage of subjects within each category will be provided for categorical data.

Individual data will be listed and sorted by treatment, subject identification number, visit, and time point.

Database lock will occur upon the completion of the study.

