5.2.2 Randomization

This study is an open-label, single-arm study (not randomized).

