5.2.11 Efficacy Analyses

SMBG values will be summarized by visit. A summary table with descriptive statistics (n, mean, median, standard deviation, minimum, and maximum) by time point relative to AfreZZA dosing will be provided. SMBG data will also be presented graphically.

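### No paired Visit 3 minus Visit 2 estimate is planned, and the visit-specific t=0 glucose, free to lie between 100 and 200 mg/dL, is not used in comparing the doses

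*Combined protocol and SAP*

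**What the plan says.** Section 1.2 (Study Rationale) says the two doses are studied "to assess whether a higher dose results in improved postprandial glucose control", and Section 3.1 describes label-based dosing compared with a titrated dose. Each subject who completes both treatment visits supplies both doses, in fixed order and without randomization (Section 5.2.2).

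Section 3.5.2.2 sets the entry condition for each challenge: "Subjects must have an SMBG value between 100 and 200 mg/dL without requiring a correction dose of bolus insulin". The t=0 reading "will be used to determine if the subject can proceed to the meal challenge and will serve as the baseline value for that visit", so a subject has two baselines, which may differ by up to 100 mg/dL. For a reading below 100 mg/dL, "the Investigator can provide 15 g of fast-acting carbohydrates and remeasure SMBG after 30 minutes".

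The primary objective (Section 2.1) is the mean change from t=0 to 15, 30, 45, 60, 90 and 120 minutes. The efficacy analysis in Section 5.2.11 opens with "SMBG values will be summarized by visit" and adds a table of n, mean, median, SD, minimum and maximum by time point, plus graphs. Section 5.2.1 lists the same statistics for all continuous variables. No model, paired difference, confidence interval or covariate appears. Section 5.2.3 states that the 20 completers were not derived statistically.

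**The concern.** The question is a within-subject one, but the planned output is two separate columns of summaries. A reader will compare the columns by eye, with no standard error for the difference and no account of where each visit started.

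Subtracting t=0 does not remove its influence unless later glucose rises one for one with it. If the slope is below 1, the visit that starts higher shows the smaller rise, whatever the dose. If raw SMBG values are compared instead, as the wording of Section 5.2.11 suggests, the visit that starts higher tends to look worse. With 20 subjects, either effect could be comparable in size to a modest dose difference. The t=0 value that would account for it is already collected.

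**Working it through.** **Inputs from the documents.** t=0 window 100 to 200 mg/dL at each visit (3.5.2.2); 20 completers (5.2.3). The sample size has no stated alpha, power, effect or SD, so there is no planning figure to reproduce.

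**Assumed inputs** (the documents give none of these). SD of t=0: 25 mg/dL. Correlation rho between a subject's two t=0 values: 0.3 to 0.5. Slope b of later glucose on t=0: 0.3 to 0.7, with 1 as the limiting case. Residual SD per visit, e: 20 or 30 mg/dL.

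**Step 1: chance difference in mean t=0.** Let dB be a subject's Visit 3 minus Visit 2 difference in t=0. Var(dB) = 2 × 25² × (1 − rho).

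- rho 0.3: variance 875, SD 29.6, SE of the mean 29.6/√20 = 6.61, 1.96 × SE = 13.0 mg/dL.
- rho 0.5: variance 625, SD 25.0, SE of the mean 5.59, 1.96 × SE = 11.0 mg/dL.

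**Step 2: what reaches the comparison.** Change scores carry (1 − b) of the difference and raw values carry b.

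- Change scores: from 0.3 × 11.0 = 3.3 to 0.7 × 13.0 = 9.1 mg/dL.
- Raw values: from 0.3 × 11.0 = 3.3 to 0.7 × 13.0 = 9.1 mg/dL. The range is the same because the assumed slopes are symmetric about 0.5.

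These are 95% limits in either direction, not expected shifts.

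**Step 3: does adjustment help precision?** Per-subject variance of the paired difference in change:

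- Unadjusted: (1 − b)² × Var(dB) + 2e².
- Adjusted: 2e² × (1 + 1/17). The last factor, 1 + 1/(n − 3), is the cost of estimating the slope.

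| b | e | rho | Unadjusted | Adjusted | Change in variance |
|---|---|---|---|---|---|
| 0.3 | 20 | 0.3 | 1228.75 | 847.06 | −31% |
| 0.3 | 30 | 0.5 | 2106.25 | 1905.88 | −9.5% |
| 0.5 | 20 | 0.3 | 1018.75 | 847.06 | −17% |
| 0.5 | 30 | 0.5 | 1956.25 | 1905.88 | −2.6% |
| 0.7 | 20 | 0.3 | 878.75 | 847.06 | −3.6% |
| 0.7 | 30 | 0.5 | 1856.25 | 1905.88 | +2.7% |
| 1.0 | 20 or 30 | any | 2e² | 2e² × 18/17 | +5.9% |

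In the first row the SE falls from √(1228.75/20) = 7.8 to √(847.06/20) = 6.5 mg/dL. With larger residual noise (paired-difference SD 40 or 60 mg/dL, t=0 SD 15 to 28.9, b 0.4 to 1.0, rho 0 to 0.5) the SE changes by between −12% (10.49 to 9.20) and +2.9% (8.94 to 9.20). A middle case (t=0 SD 20, rho 0.5, b 0.6, paired-difference SD 40) goes from 9.12 to 9.20. Adjustment pays at n = 20 only when |1 − b| × SD(dB) divided by the paired-difference residual SD exceeds 1/√17 = 0.24.

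**Step 4: bias or variance.** A simulation of 20,000 runs used independent uniform t=0 values over the window, b = 0.6, paired-difference SD 40 and a true contrast of −15. The unadjusted and adjusted estimates both averaged −15.1, with SEs of 9.62 and 9.21.

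**Step 5: which model.** A joint repeated-measures model with one common baseline slope and only a subject random intercept ignores the correlation among the six readings of the same visit. Two simulations of 300 runs each under no dose effect (assumed subject SD 20, subject-by-visit SD 17, reading SD 10, slope 0.5; other settings differed) gave false-positive rates of about 9% and 16% at a single time point. For the time-averaged contrast both gave about 49%, against a nominal 5%. The paired regression at a single time point stayed at about 3% to 5%.

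**The case against.** The strongest reply is that this is a small, open-label, descriptive proof-of-concept study with no hypothesis test. A reader might infer from this point that the plan contains a between-visit contrast that wrongly omits an adjustment. It does not: Sections 5.2.1 and 5.2.11 specify no contrast at all. That stands, and it is why the missing paired estimate comes first here and the covariate second.

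The stated measure is already a change from each visit's own t=0, so only (1 − b) of any imbalance remains, and the 100 to 200 mg/dL window limits the imbalance itself. The table by time point may well show t=0. All of this stands. However, Section 5.2.11 names SMBG values rather than changes, and neither form removes the influence of t=0 unless b is exactly 1 (changes) or 0 (values).

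A reader might also infer that chance imbalance biases the comparison. The documents give no basis for that. It is sampling variance, and a paired confidence interval would already contain it. A systematic difference is possible, since the order is fixed, progression to Visit 3 depends on the investigator's view of the Visit 2 excursion, and carbohydrate may precede t=0 at one visit and not the other. The documents do not state the direction in which the excursion guides that decision, so no sign or size can be given.

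Finally, adjustment might be taken as a sure gain in precision. Step 3 shows that it is not.

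**Conclusion.** The point holds in this form: the plan asks a within-subject question, provides no paired estimate or interval to answer it, and leaves the visit-specific t=0 value unused. With 20 subjects and the assumed inputs, chance differences in t=0 can move the comparison of change scores by up to about 3 to 9 mg/dL (95% range across the assumptions). Every input except the window and the number of subjects is assumed.

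The effect of adjustment on variance runs from a 31% reduction to a 3% increase, or about 6% if the slope is 1. The 31% needs the lowest slope, the smaller residual SD and the lower correlation together, so it should not be read as the expected gain. The paired difference with its interval is therefore the main improvement and the adjusted estimate is supportive. Adjustment for t=0 deals only with the baseline part of any systematic difference between visits. It does not remove the effects of fixed order or of selective progression to Visit 3. This is a low-cost strengthening of the analysis, not a defect that invalidates the study.

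**What to change.** Add to Section 5.2.11, before database lock:

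- For subjects with both treatment visits, report at each post-dose time point the paired Visit 3 minus Visit 2 difference in change from t=0, with a 95% CI. State how many dosed subjects lack Visit 3.
- Show mean t=0 by visit, and the mean within-subject difference, beside it.
- As a supportive estimate, regress each subject's difference in change on that subject's t=0 difference, separately by time point, and report the fitted value at a zero t=0 difference with its 95% CI. State the reference in advance: if the t=0 difference is mean-centred, the intercept merely returns the unadjusted mean, so the value must still be read at zero difference.
- If a joint model over time is preferred, give it subject-by-visit correlation or an unstructured covariance, baseline-by-time terms and a within-subject baseline term. A subject random intercept alone gives intervals that are too narrow.
- Keep the descriptive tables and graphs.

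The cost is a paragraph of text and one degree of freedom per time point in the supportive analysis. With about 10 subjects, for example within one diabetes type, the adjusted SE ranged from 8.8% smaller to 6.9% larger in the wider set of assumptions, so adjustment within subgroups should be used sparingly.
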